7.2. Interim Analyses and Summaries

No interim analysis is planned for this study.

9. APPENDICES

Appendix 1. Definition of Analysis Visit Windows

Analysis visit windows will be used for efficacy and safety data that are summarized by visit.

Visit Label	Target Day	Analysis Visit window
Baseline	Day 1 (First dose date)	Up to Day 1
Month 1	Day 30	Days 2-60
Month 3	Day 90	Days 61-135
Month 6	Day 180	Days 136-225
Month 9	Day 270	Days 226-315
Month 12	Day 360	Days 316-405
Month 15	Day 450	Days 406-495
Month 18	Day 540	Days 496—585
Month 21	Day 630	Days 586-675
Month 24	Day 720	Days 676-765
Month 27	Day 810	Days 766-855
Month 30	Day 900	Days 856-945
Month 33	Day 990	Days 946-1035
Month 36	Day 1080	Days 1036-1125
Month 39	Day 1170	Days 1126-1215
Month 42	Day 1260	After Day 1216
Follow-up		Follow-up visit and >last dose day+5

For time to event variables, there is no need to have the windowing. The actual days will be used as the event time or censored time. But the event rate at each visit will be estimated at the corresponding protocol schedule day +10 days using the Kaplan-Meier method. If more than one observation from the same subject falls into the same window, the value closest to the target day will be used as the observation for that analysis visit. All observations will, however, be included in the listings.

Analysis visit window Follow-up is defined by the visit name=FOLLOW_UP and >last dose day +5. For example, if a subject had the last dose on Day 1000 and the follow-up visit at Day 1006, then the data from Day 1006 will be treated as follow-up data instead of Month 33 data. However, if a subject had the last dose on Day 1000 and the follow-up visit at Day 1003, then the data from Day 1003 will be treated as Month 33 data.

New windowing rule for retreatment group:

Visit Label	Target Day	Analysis visit window
Baseline	Day 1 (dose escalation day)	Last observation up to Day 1 (dose escalation day)
Month 3	Day 90	Days 2-135
Month 6	Day 180	Days 136-225
Month 9	Day 270	Days 226-315
Month 12	Day 360	Days 316-405
Month 15	Day 450	Days 406-495
Month 18	Day 540	Days 496-585
Month 21	Day 630	Days 586-675
Month 24	Day 720	Days 676-765

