The investigator may schedule visits (unplanned visits) in addition to those listed on the schedule of activities table, in order to conduct evaluations or assessments required to protect the well-being of the subject.

All study visits after Baseline will have a visit window of ± 7 days.

Refer to [Appendix 9](#) for permitted alternative measures for certain study procedures in response to the ongoing global COVID-19 pandemic.

Study Procedure	Baseline	Treatment Period						
	Day 1 ¹	Month 1 (± 7 days)	Month 3 (± 7 days)	Month 6 (± 7 days)	Month 9 (± 7 days)	Month 12 (± 7 days)	Month 15 (± 7 days)	Month 18 (± 7 days)
Visit Number	1	2	3	4	5	6	7	8
Informed Consent	X							
Medical History ²	X							
Demography ¹⁰	X							
Targeted Physical Examination ³	OLE	X	X	X	X	X	X	X
Vital Signs, Including Temperature	OLE	X	X	X	X	X	X	X
Laboratory								
Hematology	OLE	X	X	X	X	X	X	X
Serum Chemistry	OLE	X	X	X	X	X	X	X
Lipid Profile, Fasting	OLE			X		X		X
Urine β -hCG ⁴	OLE	X	X	X	X	X	X	X
Dispense Stool Sample Collection Kit	X	X	X	X	X	X	X	X
Collect Stool Sample for Fecal Calprotectin ⁵	X	X	X	X	X	X	X	X
High-Sensitivity CRP	OLE	X	X	X	X	X	X	X
Tuberculosis Testing/Chest Radiograph, if necessary in Specific Countries ⁶						X		

Study Procedure	Baseline	Treatment Period						
	Day 1 ¹	Month 1 (±7 days)	Month 3 (±7 days)	Month 6 (±7 days)	Month 9 (±7 days)	Month 12 (±7 days)	Month 15 (±7 days)	Month 18 (±7 days)
HBV DNA Testing (Japan Only) ⁷	OLE	X	X	X	X	X	X	X
Endoscopic Procedure								
Flexible Sigmoidoscopy/ Colonoscopy (if preferred) ⁸	OLE			X				X
Eligibility Assessment	X							
Randomization	X							
Investigational Product Dispensing	X		X	X	X	X	X	X
Investigational Product Accountability		X	X	X	X	X	X	X
Ulcerative Colitis Assessments								
Bowel Movement Diary Data ⁹	X	X	X	X	X	X	X	X
Partial Mayo Score		X	X		X	X	X	
Mayo Score	OLE			X				X
Contraception Check For Females of Childbearing Potential	X	X	X	X	X	X	X	X
Adverse Event Monitoring	X	X	X	X	X	X	X	X
Concomitant Medication Review	X	X	X	X	X	X	X	X
Risk Factor Check for Venous Thromboembolism ¹¹	X	X	X	X	X	X	X	X

Abbreviations: ET = early termination; β -hCG = beta-human chorionic gonadotropin; OLE = open-label extension study (A3921139).

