If during the course of the study, a subject experiences an increase in clinical symptoms, such as an increase in rectal bleeding or an increase in stool frequency, then an endoscopy should be performed to assess if the subject is experiencing flare. Flare must be confirmed prior to performing any dose adjustments. In addition, subjects who experience atypical symptoms or features of their usual UC disease course or have significantly worsening disease activity assessments from the previous visit, or have the presence of risk factors such as recent antibiotic use or a recent history of *C. difficile* infection should have *Clostridium difficile* (*C. difficile*) toxin testing performed before assessing for flare and performing any dose adjustments.

Please refer to [Section 5.11](#) for tofacitinib dose adjustment guidelines and definition of flare.

Amendment 2

On 17 May 2019, the European Medicines Agency's (EMA) Pharmacovigilance Risk Assessment Committee (PRAC) issued interim recommendations on the restrictions for prescriptions of tofacitinib. These interim recommendations on the restrictions for prescriptions of tofacitinib state that patients who are at high risk of blood clots in the lungs must not be started on tofacitinib 10 mg BID, and that such patients currently taking tofacitinib 10 mg BID for any condition must be switched to alternative treatments. Updated guidance from PRAC will be provided to patients and their healthcare professionals in the European Union (EU) once PRAC has completed its review of all available data.

In light of the PRAC interim recommendations in the EU, Study A3921288 will be modified globally through protocol Amendment 2, which will involve the following updates:

1. The study investigator or designee will need to review each subject's medical history and study records, including their concomitant medications, to determine whether he/she is at high risk for developing pulmonary embolism. If he/she has any of the risk factors listed below, the subject's tofacitinib dose should be adjusted to open-label 5 mg BID (see [Section 5.11](#)).

A subject may be at high risk for pulmonary embolism if he/she:

- has heart failure;
- has inherited coagulation disorders;
- has had venous thromboembolism, either deep venous thrombosis or pulmonary embolism;
- is taking combined hormonal contraceptives or hormone replacement therapy;
- has malignancy (association is strongest with cancers other than non-melanoma skin cancers);

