5.11. Tofacitinib Dose Adjustment Guidelines

Per Amendment 2, all subjects will be reviewed for risk factors for pulmonary embolism as detailed in [Section 3](#) under Amendment 2. Per Amendment 3, all subjects will be reviewed for risk factors for venous thromboembolism as detailed in [Section 3](#) under Amendment 3. Subjects who are identified to have one or more of the risk factors for venous thromboembolism (or risk factors for pulmonary embolism per Amendment 2) will need to have their tofacitinib dose adjusted to open-label 5 mg BID.

If during the course of the study, a subject experiences an increase in clinical symptoms, such as an increase in rectal bleeding or an increase in stool frequency, then an endoscopy should be performed to assess if the subject is experiencing flare. Flare must be confirmed prior to performing any dose adjustments.

In addition, subjects who experience atypical symptoms or features of their usual UC disease course or have significantly worsening disease activity assessments from the previous visit, or have the presence of risk factors such as recent antibiotic use or a recent history of *C. difficile* infection should have *Clostridium difficile* (*C. difficile*) toxin testing performed before assessing for flare and performing any dose adjustments. In addition, subjects should be tested for *C. difficile* toxin prior to being discontinued due to worsening UC, if possible. If confirmed positive, a full course of *C. difficile* treatment, as defined by local practice, must be given to subjects with *C. difficile* infection to permit their continued participation in the study. Subjects may continue to receive tofacitinib while undergoing treatment for *C. difficile* infection. Subjects with *C. difficile* infection that meets serious infection criteria must be withdrawn from the study. Additional stool testing and treatment for other enteric pathogens is at the discretion of the investigator.

Flare is defined by meeting **one** of the following 4 criteria:

1. An increase in rectal bleeding subscore by at least 1 point and an increase in endoscopic subscore by at least 1 point; OR
2. An increase in rectal bleeding subscore by at least 2 points and an endoscopic subscore >0; OR
3. An increase in stool frequency subscore by at least 2 points and an increase in the endoscopic subscore by at least 1 point; OR
4. An increase in endoscopic subscore by at least 2 points.

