Once the subject is confirmed to meet the definition for flare, documented by site read endoscopy, the investigator may adjust the dose through the IRT system provided that the subject does not have any of the risk factors for venous thromboembolism (see [Section 7.3.6](#)). Once confirmed by the investigator, subjects may have a dose increase to 10 mg BID or remain on 10 mg BID, depending on their initial treatment assignment. Dose adjustments for confirmed flare will not be permitted prior to the Month 1 study visit.

Subjects who develop one or more of the risk factors for venous thromboembolism during the study will not be permitted to increase their tofacitinib dose to 10 mg BID should they experience a flare of their UC.

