5.3. Methods to Manage Missing Data

5.3.1. Efficacy Endpoints

For binary efficacy endpoints derived from total Mayo score or partial Mayo score, subjects with missing scores in an analysis window will be considered as non-responders.

For continuous endpoints that are measured repeatedly over time, the missing values will be handled in a linear mixed effects model where missing values are assumed to be missing at random.

For continuous endpoints based on total Mayo score and modified Mayo score, data collected after baseline to Month 6 will be considered as Month 6 if a subject has missing data at Month 6; data collected after Month 6 to Month 18 will be considered as Month 18 if a subject has missing data at Month 18; data collected after Month 18 to Month 30 will be considered as Month 30 if a subject has missing data at Month 30; data collected after Month 30 to Month 42 will be considered as Month 42 if a subject has missing data at Month 42. The description of the handling of missing data within individual components of the Mayo score is described in an [Appendix 2.1](#).

Subjects who drop out or complete the study without meeting the flare criteria will be censored at the last visit with Mayo score assessment for endpoint of time to loss of remission (flare).

Descriptive summary will also be presented based on observed data for efficacy data.

For the subgroup of subjects who are initially assigned to tofacitinib 5 mg BID and later are retreated with tofacitinib 10 mg BID, missing data will not be imputed.

For fecal calprotectin and hs-CRP, the missing values will be handled in a linear mixed effects model where missing values are assumed to be missing at random.

In addition, for hs-CRP, assayed values below the limit of quantification (BLQ) will be set to 10% less than the given assay lower limit for the specific biomarker. In listings BLQ values will be reported as “<LLQ” where LLQ will be replaced with the value for the lower limits of quantification. Assay values will be set to missing if a value has been collected as ND (ie, not done) or NS (ie, no sample).

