5.3.3. Method of Handling the Data after Dose Escalation or Dose Reduction

For this study, subjects may have a dose escalation to 10 mg BID due to flare or dose reduction to 5 mg BID due to PE risk factors. The data after the dose change for the dose group and regimen group are handled as follows.

- For Tofacitinib 10 mg BID dose group: For subjects with dose reduction due to PE risk factor, data collected after the dose reduction will not be included in the safety and efficacy analyses, and last observation carried forward (LOCF) will be used for binary and continuous efficacy endpoints. The subjects will be considered as censored at the dose reduction time for endpoint of time to loss of remission (flare).
- For Tofacitinib 5 mg BID dose group: data collected after the dose escalation (with or without dose reduction due to PE risk factor after the dose escalation) from tofacitinib 5 mg BID to 10 mg BID will not be included in the safety and efficacy analyses. The subjects will be treated as non-responders for any visit after the dose escalation visit for binary efficacy endpoints. For continuous efficacy endpoints, the data collected for any visit after the dose escalation visit will be considered as missing. For time to loss of remission (flare), the subject will be considered as having an event at the visit with a dose escalation if the event criteria are met or having a censored time at the visit with a dose escalation if the event criteria are not met.
- For Tofacitinib 10 mg BID regimen group: For subjects with dose reduction due to PE risk factor, data collected after the dose reduction will be included in the safety and efficacy analyses.

- For Tofacitinib 5 mg BID regimen group: Data collected after the dose escalation will be included in the analyses. For subjects with dose reduction due to PE risk factor after the dose escalation, data collected after the dose reduction will be included in the safety and efficacy analyses.

The following table provides some examples on how to handle the data after the dose escalation for flare and dose reduction for risk factors for PE:

Table 2 Examples on How to Handle Data After Dose Change

Examples	Dose group		Regimen group	
	Safety analysis	Efficacy analysis	Safety analysis	Efficacy analysis

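### For partial and modified partial Mayo change scores, the closest-to-target window rule can drop the flare value that led to escalation from 5 mg, which tilts the dose comparison toward 5 mg

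*SAP*

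**What the plan says.** **Flare assessment.** When symptoms increase, Protocol Section 3 says "then an endoscopy should be performed to assess if the subject is experiencing flare", and Section 5.11 repeats this. Escalation is possible from Month 1 onward: "Dose adjustments for confirmed flare will not be permitted prior to the Month 1 study visit". The Schedule of Activities allows unplanned visits and sets the timing of planned ones: "All study visits after Baseline will have a visit window of ± 7 days".

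**Windows.** SAP Appendix 1 cuts the windows midway between target days. Month 6, for example, has target Day 180 and window Days 136-225. For two values in one window the rule is: "If more than one observation from the same subject falls into the same window, the value closest to the target day will be used"; the other appears only in listings.

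**After escalation.** For the 5 mg dose group, SAP 5.3.3 says: "For continuous efficacy endpoints, the data collected for any visit after the dose escalation visit will be considered as missing". The exclusion starts after the escalation visit, so that visit's own value is meant to count.

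**Missing data.** SAP 5.3.1 says: "For continuous endpoints that are measured repeatedly over time, the missing values will be handled in a linear mixed effects model", under a missing-at-random assumption. A separate rule in 5.3.1 lets interim total and modified Mayo scores stand in for a missing Month 6, 18, 30 or 42 score. It does not cover partial Mayo, modified partial Mayo, fecal calprotectin or hs-CRP.

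**The concern.** Missing at random is arguable here only if the value that led to escalation is in the model. When the window rule removes it, the 5 mg subject's record shows the last scheduled score, typically one in remission, followed by a gap that the model fills from that history.

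The loss is not symmetric. The closest-value rule also applies to a 10 mg subject who flares, but that subject stays on 10 mg, and later scheduled scores remain in the dose-group analysis. Worsening in the 10 mg group can therefore still be seen, while part of the worsening in the 5 mg group cannot. The binary endpoints treat the same escalated subject as a non-responder, so the binary and continuous results of one dose comparison could disagree because of windowing alone.

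**Working it through.** The plan states no figure for this point, so there is none to reproduce first.

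**Step 1. Share dropped, from the windows alone.** Inputs are the Appendix 1 targets and cut-offs, and flare days 31 to 1259 (after Month 1, before Month 42). Assume that visits fall on target, every flare is assessed between visits, timing is even and post-escalation data are removed first. A flare value is lost if it falls in the later half of a window whose scheduled visit has already taken place:
- after Month 1: Days 31-60, 30 days;
- after each of the 13 visits from Month 3 to Month 39: 45 days, so 13 × 45 = 585.

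Share = (30 + 585) / 1,229 = 615 / 1,229 = 50.0%.

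**Step 2. Visit timing of ±7 days.** A flare within a few days of target can be closer than the scheduled visit and so be kept. Simulation with this jitter gives 47.0%.

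**Step 3. Other timing assumptions.**
- If half of flares are confirmed at a scheduled visit, those lose nothing: 0.5 × 47% = 23.5%. Simulations gave about 20-27%.
- If flares cluster late or early within intervals, the share runs from 14% to 79%.
- If windowing is done before the exclusion, the next scheduled visit can displace the flare value and then be removed itself. The share becomes 93-100%. The SAP does not state the order.

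**Step 4. Effect on the average 5 mg minus 10 mg difference in partial Mayo change, to Month 18.** The model is a random-intercept mixed model with baseline, visit and group-by-visit terms. Flare rates, score size and persistence are assumptions. The 27.3% yearly rate is 100% − 72.7%, the 12-month remission figure after reduction to 5 mg in Protocol Section 1.2, and is used only as an illustration.

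| Assumed flares, 5 mg v 10 mg | As written | Flare value kept | Complete data, staying on 5 mg | Share due to window rule |
|---|---|---|---|---|
| 35% v 18% over 18 months, score 4.5 | 0.01 | 0.15 | 0.34 | 0.14/0.33 = 42% |
| 25% v 12% over 18 months | 0.02 | 0.11 | 0.26 | 0.09/0.24 = 38% |
| 27.3% v 15% per year, rise of 2 | -0.105 | -0.011 | 0.171 | 0.094/0.276 = 34% |
| 27.3% v 15% per year, rise of 4 | -0.204 | -0.004 | 0.346 | 0.200/0.550 = 36% |
| 40% v 20% per year, rise of 2 | -0.116 | 0.038 | 0.281 | 0.154/0.397 = 39% |
| 40% v 20% per year, rise of 4 | -0.223 | 0.104 | 0.566 | 0.327/0.789 = 41% |

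Share = (kept − as written) / (complete − as written). In a further run, with 35% v 18% flares whose scores faded over time, the three values were 0.01, 0.17 and 0.17, so keeping the flare value closed the whole gap.

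**Step 5. Carry-forward bound.** Carrying the escalation-visit value to later visits gave 0.59 against 0.34 (first row) and 0.45 against 0.26 (second row), so it overshoots.

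**The case against.** **Reach.** A reader might infer that every mixed model loses the flare, or that the main result is biased. The documents do not support this. The primary endpoint and the other binary endpoints count escalated subjects as non-responders. Time to flare uses actual days without windows. Total and modified Mayo change have the 5.3.1 fill-in rule, and total Mayo change at Month 6 uses ANCOVA. Only 9-11% of flare values for these two scores share a window with an earlier full-Mayo visit. That falls to zero if the fill-in period is read as starting at the visit rather than at the end of its window. This objection stands and limits the point to secondary change scores; SAP 5.1 also says that no formal hypotheses are tested.

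**Whether a flare value exists.** The rule cannot discard what was never recorded. The flare criteria use rectal bleeding, stool frequency and endoscopy, so modified partial Mayo should usually be available. Partial Mayo also needs the physician's global assessment, which is not expressly required at an unplanned flare visit. Stool samples at flare are requested only when possible, and hs-CRP is listed at scheduled visits only. This stands, and biomarkers belong here only where a sample was taken.

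**Size.** If half of flares are confirmed at scheduled visits, a small simulation put the shift at about 0.04-0.08, against a model standard error near 0.09-0.10. Where flares persist, most of the shortfall comes from setting post-escalation data to missing. That choice is stated in the protocol and fits the objective of remaining on 5 mg. This also stands.

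**10 mg group.** Flaring 10 mg subjects who start other UC therapy are withdrawn, so not all keep later values. The asymmetry holds for those who stay.

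The regimen analysis and the retreatment summary do use the flare-time or later data, but they do not repair the dose-group model.

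**Conclusion.** The concern holds for change from baseline in partial and modified partial Mayo score, and for fecal calprotectin or hs-CRP only where a sample was taken at flare. For these, the closest-to-target rule works against SAP 5.3.3, which leaves the escalation-visit value in. The resulting bias in the dose comparison favours 5 mg.

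With even flare timing and exclusion before windowing, about 47% of flare values are dropped if all flares are assessed between visits, and about 20-27% if half are confirmed at scheduled visits; across timing assumptions the range is 14-79%. Keeping the value moved the average partial Mayo difference by roughly 0.05-0.16 in most scenarios, and by up to 0.33 under the highest assumed rates and score rise. Where flares persist, that is roughly 35-40% of the shortfall, and the post-escalation missing rule accounts for the rest. The sign and size of the as-written estimate changed between sets of assumptions, so the direction of the bias is firmer than its magnitude.

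A reader might infer that half of all flares go unseen or that the conclusion on Month 6 remission is at risk. Neither follows: the first needs every flare to be assessed between visits, and the second concerns an endpoint that this rule does not bias.

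**What to change.** In SAP Appendix 1, for the dose-group analysis of these continuous endpoints:
- apply the post-escalation exclusion before windowing, and say so;
- use the value from the confirmed-flare (dose-adjustment) visit as the observation for its window, whatever its distance from target, with the same rule in both dose groups.

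With this rule the share of recorded flare values lost for partial Mayo falls to 0%. The part of the shortfall that comes from setting post-escalation data to missing remains.

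Optionally, add a supportive run that carries the escalation-visit value to later visits in the 5 mg dose group. Label it a conservative bound, because it overshot the complete-data value in simulation.

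The cost is a short addition to the windowing rule and, if wanted, one extra run. Data collection and clinical conduct do not change. The small downside is that the value for that window lies further from its target day.
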